### 10.1.2 Serious Adverse Events (SAEs)

Each AE must be classified by the investigator as SERIOUS or NONSERIOUS. An AE that meets 1 or more of the following criteria/outcomes is classified as serious:

- Death
- Life-threatening (see paragraph below on Life-threatening)
- In-patient hospitalization or prolongation of existing hospitalization (see paragraph below on Hospitalization)
- Persistent or significant disability/incapacity (see paragraph below on Disability)
- Congenital anomaly/birth defect
- Is considered a medically important event not meeting the above criteria, but which may jeopardize a subject, or may require medical or surgical intervention to prevent one of the criteria listed in this definition.

Serious also includes any other event that the investigator or sponsor judges to be serious. If there is any doubt whether the information constitutes an AE or SAE, the information is to be treated as an SAE.

**Life-threatening** – Any event in which the subject was at risk of death at the time of the event; 'life-threatening' does not refer to an event which hypothetically might have caused death if it were more severe.

**Hospitalization** – Hospitalization is defined as an overnight admission with observation of a minimum of 24 hours. A hospitalization planned before the start of the study for a pre-existing condition that has not worsened during the AE reporting period does not constitute an SAE.

**Disability** – Defined as a substantial disruption in a person's ability to conduct normal life functions.

## 10.2 Eliciting Adverse Event Information

The investigator is to report all directly observed AEs and all AEs spontaneously reported by the study subject. In addition, each study subject will be questioned about AEs at each visit following the initiation of treatment.

## 10.3 Reporting

Each AE is to be classified by the investigator as SERIOUS or NONSERIOUS.

All AEs that occur in study subjects during the AE reporting period specified in the protocol must be reported, whether or not the event is considered related to study medication.

### 10.3.1 Reporting Period

The reporting period for all non-serious AEs and all SAEs not related to protocol procedures begins upon receiving the first dose of study medication and ends at the final protocol-required visit.

**SAEs that are assessed by the investigator to be related to protocol procedures (eg, ESA washout) must be reported after signing of the informed consent form.**

In addition, SAEs that occur after the protocol-defined AE reporting period that are considered to be related to the study medication should be recorded and reported to the sponsor's medical monitor or CRO designee.

### 10.3.2 Reporting AEs

NONSERIOUS AEs are to be reported on the AE CRFs.

### 10.3.3 Reporting SAEs

Any SAE, regardless of causal relationship, must be reported to the sponsor's medical monitor/medical director or CRO designee **within 24 hours** after the investigator becomes aware of the SAE. Compliance with this time requirement is essential so that the sponsor may comply with its regulatory obligations.

The initial SAE report should be completed as fully as possible but should contain, at a minimum:

- Subject number/ID, sex, and age/date of birth
- The date of report
- Name of the reporter
- Description of the event, including event term(s), seriousness criteria, and a clinical summary of the event
- Causality assessment

Information about all SAEs (either initial or follow-up information) should be collected and recorded in English on the SAE Report Form. The investigator must assess the relationship to each specific component of the study treatment. If the event meets serious criteria, SAE Report Form should be sent to the CRO via email or fax, or the investigator should call the CRO SAE

hotline within 24 hours of being made aware of the SAE (reference the site manual for contact information).

The investigator must report follow-up information relating to an SAE to the sponsor's medical monitor/medical director or CRO designee within 24 hours of awareness by submitting a new SAE Report Form. The subject should be observed and monitored carefully until the condition resolves or stabilizes.

All deaths are to be thoroughly investigated and reported. Autopsy reports are to be obtained, if possible, and sent to the CRO via email or fax.

The sponsor and/or its designee are responsible for reporting SAEs to all applicable regulatory agencies and the central ethics committees within the required timeline.

The investigators are responsible for submitting required safety information to their local Institutional Review Board (IRB) or Independent Ethics Committee (IEC) per local regulations. This information includes but is not limited to, any safety alert letter received from the sponsor and any SAEs occurring at their investigative site.

#### **10.3.4 Relationship to Study Medication**

The causal relationship of the AE to study medication will be assessed by both the investigator and the sponsor.

The assessment of causal relationship to study drug should be **evidence-based**, and not based on the premise that all AEs are possibly causally related to study drug until proven otherwise.

Examples of evidence that would suggest a causal relationship between the drug and the AE include the occurrence of an AE that is uncommon and known to be strongly associated with drug exposure (eg, angioedema, hepatic injury, Stevens-Johnson Syndrome), or an AE that is uncommon in the population exposed to the drug.

The causal relationship of the AE is assessed using a binary system, and AEs are classified as either 'related' or 'unrelated':

**Related:** There is 'reasonable possibility' that the drug caused the AE. The AE follows a reasonable temporal sequence from the time of drug administration. There is supportive evidence (facts) to suggest a possible causal relationship, irrespective of the degree of certainty between the observed AE and the drug.

**Unrelated:** An AE does not follow a reasonable temporal sequence from administration of the product and/or there is no reasonable possibility that the drug caused the AE. This assessment includes situations where the AE is related to other factors such as the subject's clinical state, other therapeutic interventions, or concomitant drugs administered to the subject.

Default assessments using the 'related' category without supportive evidence for a causal relationship to study drug is generally uninformative and does not contribute meaningfully to the development of the safety profile of the drug or to subject protection.

Investigators are encouraged to choose the most plausible cause for the event(s) from the following list: Medical history, lack of efficacy/worsening of treated condition, study treatment, other treatment (concomitant, or previous), withdrawal of study treatment, administration error, protocol-related procedure, others (specify).

### 10.3.5 Severity

The investigator will assess each AE as either MILD, MODERATE, or SEVERE using the following guidelines to describe the maximum severity of the AE:

- MILD: Does not interfere with subject's usual function.
- MODERATE: Interferes to some extent with subject's usual function
- SEVERE: Interferes significantly with subject's usual function.

Note that a **severe** AE is not necessarily a **serious** AE. For example, a headache may be severe in intensity, but would not be classified as serious unless it met 1 of the criteria for serious events listed above.

### 10.3.6 Follow-Up of Unresolved Events

All AEs should be followed until they are resolved or the investigator assesses them as chronic or stable or the subject's participation in the trial ends.

In addition, all SAEs and those non-serious events assessed by the investigator as related to the study medication should continue to be followed even after the subject's participation in the trial is over. Such events should be followed until they resolve or until the investigator assesses them as "chronic" or "stable." Resolution of such events is to be documented on the appropriate CRF.

### 10.3.7 Special Situations

Certain safety events, called 'Special Situations', that occur in association with study medication(s) may require reporting. These Special Situations include, but are not limited to, the following:

- Overdose of the medicinal product
- Suspected abuse/misuse of the medicinal product
- Inadvertent or accidental exposure to the medicinal product
- Medication error involving the medicinal product (with or without subject/patient exposure to the sponsor's medicinal product, eg, name confusion)
- Drug-drug interaction

Special situations should be reported on the Special Situations CRF whether they result in an AE/SAE or not. Special situations with associated AE/SAE should also be reported on the corresponding AE/SAE forms, following applicable AE or SAE process.

## 10.4 Exposure In Utero

A pregnancy in a female subject must be confirmed by a positive serum  $\beta$  human chorionic gonadotropin ( $\beta$ -HCG) test.

The study medication should be immediately discontinued once the pregnancy of a female study participant has been confirmed.

If any study participant becomes or is found to be pregnant while receiving a study medication or within 30 days of discontinuing the study medication, the pregnancy must be recorded on the

Pregnancy Reporting Form/Exposure In Utero Form within 24 hours of awareness of the pregnancy and sent to the CRO via email or fax (reference the site manual for contact information).

The Pregnancy Reporting Form/Exposure In Utero Form must be completed with all known information regarding the pregnancy at the time of reporting. Investigative site personnel will update the form with additional information regarding the pregnancy and the outcome of the pregnancy as it becomes available until the outcome of the pregnancy is reported.

Pregnancy during this time frame of the female partner of a male subject should also be reported.

The investigator will follow the subject (or female partner of a male subject) until completion of the pregnancy. If the outcome of the pregnancy meets the criteria for immediate classification as an SAE (ie, spontaneous abortion, stillbirth, neonatal death within 1 month of birth, or congenital anomaly [including that in an aborted fetus]), the investigator should follow the procedures for reporting an SAE within 24 hours of awareness. A pregnancy in and of itself is not considered an AE; however, unexpected complications are considered AEs.

Additional information about pregnancy outcomes follows:

- Note that “spontaneous abortion” includes miscarriage and missed abortion.
- Neonates should be followed through gestational age of 46 weeks.
- Follow-up information includes the course, duration and the outcome of the pregnancy and the neonate’s health.
- All neonatal deaths that occur within 1 month of birth should be reported, without regard to causality, as SAEs. In addition, any infant death after 1 month that the investigator assesses as related or unrelated to the in utero exposure to the study medication should also be reported.
- In the case of a live birth, the “normality” of the newborn can be assessed at time of birth.
- The “normality” of an aborted fetus can be assessed by gross visual inspection unless there are pre-abortion laboratory findings suggestive of a congenital anomaly.

## **11 DATA ANALYSIS**

An overview of the statistical approach to the primary endpoint and safety analyses are provided below. The details of the planned analysis of the primary endpoint as well as the planned analyses of secondary endpoints, PK, PD, and safety will be documented in the statistical analysis plan (SAP).

### **11.1 Primary Endpoint – Mean Change in Hb from Pre-treatment to the End of the Primary Efficacy Period (Week 6)**

The primary objective of this study is to evaluate the dose-response relationship between oral vadadustat once daily dosing for 6 weeks and the change in Hb in Japanese subjects with anemia secondary to DD-CKD; this is to define the starting dose for use in Phase 3 clinical studies in Japan.

The primary endpoint is the mean change in Hb from pre-treatment to the end of the primary efficacy period (Week 6). Pre-treatment Hb is defined as the average of 3 Hb values obtained prior to treatment based on 2 qualifying screening Hb values and the Hb value at the baseline visit (Day 1).

## 11.2 Primary Efficacy Analysis and Sample Size Determination

An analysis of covariance (ANCOVA) model will be used to compare change from pre-treatment in Hb between the three vadadustat dosing groups and the placebo group. The model will include treatment assignment (3 dosed groups and one placebo group) and pre-treatment Hb value as a covariate. A step-down procedure will be used to control the overall type I error rate for the multiple comparisons. Testing of the highest dose compared with placebo will be conducted first. If and only if this comparison is significant, then testing will proceed to comparison of the next lower dose and placebo, and so on. Thus, no multiplicity adjustment will be needed for this analysis.

The sample size and power calculations are based on results from Study AKB-6548-CI-0005 that was conducted in the United States and evaluated vadadustat in patients with anemia secondary to non-dialysis-dependent CKD. It is reasonable to extrapolate these data to the current study based on the following findings:

- PK parameters of vadadustat are similar between CKD patients who are receiving hemodialysis (Study AKB-6548-CI-0009) and CKD patients who are not receiving dialysis (Study AKB-6548-CI-0003)
- Hemodialysis procedure has no significant impact on the PK of vadadustat (Study AKB-6548-CI-0009)
- The dose range of 150-600 mg of vadadustat to be used in the current study has been shown to be generally well-tolerated, and efficacious in raising and/or maintaining Hb at the desired target level in CKD patients who were either on hemodialysis (Study AKB-6548-CI-0011) or CKD patients who were not on dialysis (Studies AKB-6548-CI-0005 and AKB-6548-CI-0007)

The target enrollment will be approximately 48 subjects for the study with 12 subjects enrolled in each of the 4 treatment groups.

The study is powered based on a comparison of the highest dose vadadustat group (600 mg daily) and the placebo group.

Based on the results from Study AKB-6548-CI-0005 that was conducted in the United States and evaluated vadadustat in patients with anemia secondary to NDD-CKD, it is assumed that the expected mean Hb changes from pre-treatment to Week 6 will be approximately 0 mg/dL for the placebo group and 1.35 g/dL for the highest dose vadadustat group (600 mg daily).

Based on the results from Study AKB-6548-CI-0011 that was conducted in the United States and evaluated vadadustat in patients with anemia secondary to DD-CKD, it is assumed that the common Hb standard deviation will be 0.9 g/dL across treatment groups. In addition, a dropout rate of 10% is assumed. With these assumptions, the study with n=12 subjects per group will have >85% power to detect the difference between treatment group and control group, at 2-sided alpha of 0.05.

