A completed Phase 2b, randomized, double-blind, placebo-controlled study to assess the hematologic PD response, safety, and tolerability of oral vadadustat for 20 weeks was performed in 210 subjects with anemia associated with NDD-CKD (AKB-6548-CI-0007). Subjects were assigned to a study group based on their ESA status at screening (naïve, previously treated, or actively treated) and were randomized 2:1 to receive either vadadustat at a starting dose of 450 mg/day or placebo. The dose of vadadustat was adjusted based on Hb levels and changes in Hb. A significantly higher proportion of subjects with a successful Hb response at the end of treatment was observed with vadadustat treatment when compared with placebo ( $p < 0.0001$ ). The dosing algorithm was effective in minimizing excessive Hb levels ( $>13.0$  g/dL) and a consistent and sustained improvement in iron mobilization was observed with vadadustat treatment. The safety profile of vadadustat in this study was generally consistent with that observed in prior clinical studies.

Based on the Phase 1 and Phase 2 study results, vadadustat is a suitable candidate for continued development as a treatment for anemia in patients with CKD.

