**Figure 3: Overview of Study Design**

\* For subjects who develop an excess Hb response during the primary efficacy period, the number of tablets of study drug will be decreased (see Section 8.2.4). For these subjects, the number of tablets of vadadustat initiated at the Week 6 visit will be lower than indicated.

The study will include the following periods:

- Eligibility screening period (see Section 9.1 for additional information regarding screening visits and ESA washout period for subjects who were prescribed ESAs at study entry)
  - Up to 4 weeks for subjects who were not prescribed ESAs prior to study entry (Day -28 to Day 0)
  - Up to 6 weeks for subjects who were prescribed epoetin alfa, epoetin beta, and epoetin kapp prior to study entry (Day -42 to Day 0)
  - Up to 8 weeks for subjects who were prescribed darbepoetin alfa prior to study entry (Day -56 to Day 0)
  - Up to 11 weeks for subjects who were prescribed epoetin beta pegol prior to study entry (Day -77 to Day 0)
- Primary efficacy period (6 weeks; Weeks 1 to 6)
- Dose adjustment and maintenance period (10 weeks; Weeks 7 to 16)
- Follow-up period (2 weeks; Weeks 17 and 18)

Subjects will participate in a screening period to determine study eligibility. Subjects who have not recently received ESA therapy will participate in 2 screening visits. Subjects who have recently received ESA therapy and otherwise meet eligibility criteria will be required to washout

from ESA therapy prior to evaluation of screening Hb, and will participate in 3 screening visits (see [Section 7.2](#)).

Eligible subjects will be randomized following the screening period using a central randomization system. Subjects will be randomized 1:1:1 to receive 1, 2, or 4 tablets at their baseline visit (Day 1). Within each tablet-count group, subjects will be randomized 3:1 to receive vadadustat (150, 300, or 600 mg vadadustat) or placebo. See [Section 8.2.2](#) for information regarding the randomization scheme.

Study drug treatment will be administered during a 6-week primary efficacy period. See [Section 8.2.4](#) for information on study drug administration. The primary efficacy period includes fixed-dose treatment to establish a dose-response relationship. However, if Hb level increases rapidly or if the Hb levels exceeds 13 g/dL, the study drug dose can be decreased or interrupted (see [Section 8.2.4](#)).

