### 7.2 Inclusion Criteria

Subjects must meet the following inclusion criteria to be eligible for study participation:

1. Male and female Japanese subjects (20 years or older)
2. Receiving chronic maintenance hemodialysis for end-stage kidney disease for at least 8 weeks prior to screening
3. ESA status and screening Hb that meet one of the following criteria:
  - a. For subjects who are not being treated with ESAs: Hb <10.0 g/dL, average of 2 measurements obtained during screening. These subjects must be off ESAs for at least the following periods of time prior to screening visit 1 (refer to [Appendix C](#) for examples):
    - i. 2 weeks for epoetin alfa, epoetin beta, or epoetin kappa;
    - ii. 4 weeks for darbepoetin alfa;
    - iii. 8 weeks for epoetin beta pegol.
  - b. For subjects who are being treated with ESAs: Hb <10.0 g/dL, average of 2 measurements obtained during screening after the protocol-defined ESA washout period. These subjects must washout ESA therapy for the following periods of time during the screening period, beginning at screening visit 1 and prior to screening visit 2 (refer to [Appendix C](#) for examples):
    - i. 2 weeks for epoetin alfa, epoetin beta, and epoetin kappa;
    - ii. 4 weeks for darbepoetin alfa;
    - iii. 8 weeks for epoetin beta pegol.
4. Serum ferritin  $\geq 50$  ng/mL during screening
5. Transferrin saturation (TSAT)  $\geq 20\%$  during screening
6. Folate and vitamin B12  $\geq$  lower limit of normal during screening
7. For subjects who are receiving oral or intravenous iron supplementation, the dose of iron supplementation must be stable for at least 28 days prior to the screening period. For subjects who are not receiving oral or intravenous iron supplementation, no iron

supplementation may have been administered for at least 28 days prior to the screening period.

8. Understands the procedures and requirements of the study and provides written informed consent and authorization for protected health information disclosure

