### **8.2.2 Randomization**

Prior to start of dosing on Day 1, a central randomization system will be used to randomize subjects at a 1:1:1 ratio to receive 1, 2, or 4 tablets.

Within each tablet-count group, subjects will be randomized 3:1 to receive vadadustat or placebo as shown in [Figure 5](#).

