- Adverse event review: Beginning with the first dose of study medication and through the follow-up visit, the investigator and study personnel will review each subject's laboratory and clinical evaluation findings and query the subject directly regarding AEs. Additional information is provided in [Section 10](#) and follow-up of unresolved AEs, serious adverse events (SAEs), and non-serious events is described in [Section 10.3.6](#).
- Rescue therapy (ESA rescue and RBC transfusion) review: Beginning with the first post-baseline visit (after Day 1) and through the follow-up visit, the investigator and study personnel will review whether a subject received rescue therapy (ESA rescue or RBC transfusion).
- Concomitant medication review: All medications taken within 30 days prior to the start of study medication and through the final study visit should be recorded on the appropriate CRF. In addition, the ESA and iron treatment regimen prior to randomization and date of last dose will be recorded.

At each study visit, subjects will be asked whether they have started or discontinued any medication since their previous study visit. This includes single use or as needed medication use. All medications and treatments, including vitamin supplements, over-the-counter medications, and oral herbal preparations must be recorded in the CRFs.

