4.7.1.2 Adjustments for Covariates

The primary efficacy analysis will be adjusted for the pre-treatment measure of primary efficacy variable.

An ‘unadjusted’ sensitivity analysis will be performed to assess the robustness of the study conclusion.

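### Prior ESA exposure is recorded and structures screening, but no analysis uses it; pre-specifying one baseline factor would be a cheap gain in precision

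*Protocol*

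**What the plan says.** **Model.** Protocol 11.2 and SAP 4.7.1 give the same two terms: "The model will include treatment assignment (3 dosed groups and one placebo group) and pre-treatment Hb value as a covariate". SAP 4.7.1.2 confirms it: "The primary efficacy analysis will be adjusted for the pre-treatment measure of primary efficacy variable". The sensitivity analyses are an unadjusted ANOVA and the per-protocol population. The dose-response regression in SAP 4.7.1 has dose as its only regressor. SAP 4.7.1.6 plans no subgroup analysis.

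**Randomisation.** Protocol 8.2.2 describes two steps: "a central randomization system will be used to randomize subjects at a 1:1:1 ratio to receive 1, 2, or 4 tablets", then "Within each tablet-count group, subjects will be randomized 3:1 to receive vadadustat or placebo". It names no stratification factor.

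**ESA status in the design.** Inclusion criterion 3 (Protocol 7.2) has two branches. Under 3a, subjects are already off ESA. Under 3b, ESA is withdrawn during screening and Hb must qualify on the "average of 2 measurements obtained during screening after the protocol-defined ESA washout period". Protocol 6.1 adds: "Subjects who have recently received ESA therapy and otherwise meet eligibility criteria will be required to washout". Screening length, number of screening visits, Sections 9.4 and 9.5, and Appendices A and B all follow this split.

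**Data.** Protocol 9.3.1 states that "the ESA and iron treatment regimen prior to randomization and date of last dose will be recorded". SAP 4.5 does not name ESA history among its baseline summaries. Its prior-medication table looks back 30 days from first dose.

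**The concern.** The endpoint is a change in Hb over six weeks. Two subjects can have the same pre-treatment Hb while one is stable and the other is still drifting down after ESA withdrawal. The covariate averages two screening values and Day 1, so it captures level but not direction. If recent withdrawal does carry a continuing trend, that trend goes into the Week 6 change. An arm that happens to hold more such subjects will then look worse than it should.

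The primary objective is to choose a Phase 3 starting dose from arms of 12. The current text assumes an effect for 600 mg but none for 150 or 300 mg, so one cannot presume that a shift of a given size is small against those contrasts. The imbalance might also go unnoticed, because no named baseline table would show it.

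**Working it through.** **Inputs from the documents.** 12 per arm; difference 1.35 g/dL (600 mg v placebo); SD 0.9 g/dL; dropout 10%; two-sided alpha 0.05 (Protocol 11.2).

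**Assumed inputs.** Share of subjects with recent ESA use, p. Effect of recent ESA use on Week 6 Hb change given pre-treatment Hb, g. The documents give neither, so ranges are shown.

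**1. The plan's own power.** Evaluable per arm: 12 × 0.9 = 10.8. SE of a difference: 0.9 × √(2/10.8) = 0.387 g/dL. Noncentrality: 1.35/0.387 = 3.49. Power is 93.6% by the normal approximation, 91.2% by the t distribution with two-group degrees of freedom, and 92.5% with four-group degrees of freedom (4 × 10.8 − 5 = 38.2). The stated bound of more than 85% holds.

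**2. Chance of imbalance.** Two arms, each Binomial(12, p):

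| p | P(differ by ≥3 of 12) |
|---|---|
| 0.5 | 31% |
| 0.7 | 26% |
| 0.8 | 20% |
| 0.9 | 8% |
| 0.95 | 2% |

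Drawing the two arms without replacement from 48 gives 31% at p = 0.5 and 24% at p = 0.75.

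**3. Size of the shift.** Shift = g × 3/12. For g = 0.3, 0.6 and 0.9 g/dL this is 0.075, 0.15 and 0.225 g/dL, or 0.2, 0.4 and 0.6 of the SE in step 1.

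**4. Variance explained.** R² = g²p(1−p)/0.9². Equivalent extra subjects = 48 × [1/(1−R²) − 1].
- g = 0.3, p = 0.7: R² = 0.09 × 0.21/0.81 = 2.3%, about 1 subject.
- g = 0.6, p = 0.5: R² = 0.36 × 0.25/0.81 = 11.1%, 6 subjects.
- g = 0.9, p = 0.5: R² = 0.81 × 0.25/0.81 = 25%, 16 subjects.
- p = 0.9, g from 0.3 to 0.9: 0.5 to 4.7 subjects.

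**5. Power with the term added.** 10.8 per arm, one degree of freedom fewer, residual SD = √(0.81 − p(1−p)g²), p from 0.25 to 0.75:
- g = 0: 92.4%, against 92.5% without the term.
- g = 0.5: 93.8-94.2%.
- g = 1.0: 97.2-98.3%.

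**6. Type I error, 600 mg v placebo.** Simulation with four arms of 11, p = 0.5, 12,000 runs per setting. Over all trials it is 0.049-0.051, with or without the term. In the roughly 13% of trials where the two arms differ by 4 or more of 11:

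| g (g/dL) | planned model | with ESA term |
|---|---|---|
| 0.5 | 0.068 | 0.052 |
| 1.0 | 0.153 | 0.053 |

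**7. Would the baseline tables show it?** Minimum time from last ESA dose to Day 1 for subjects washed out in screening is the washout plus 4 days plus 4 days (Protocol 9.1):
- epoetins: 14 + 8 = 22 days
- darbepoetin alfa: 28 + 8 = 36 days
- epoetin beta pegol: 56 + 8 = 64 days

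The last two lie outside the 30-day look-back in SAP 4.5.

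**The case against.** **The two branches are not cleanly different.** Criterion 3a admits former ESA users who have been off for at least 2, 4 or 8 weeks before screening visit 1. The second Appendix C example for untreated subjects, reproduced in the summary of changes, shows such a case. Criterion 3b requires the same minimum before screening visit 2. Each is that branch's first qualifying Hb, and the later spacing rules are the same. For a given ESA class, the minimum ESA-free time is therefore equal in both branches. A plain flag for washout during screening would put some recent stoppers together with never-users. This stands and shapes the fix.

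**The mechanism is unproven.** Nothing in the documents shows Hb still falling at Day 1. The planning assumption is about zero change on placebo, and pre-treatment Hb, measured after washout, absorbs differences in level. This also stands. A reader might infer that washed-out subjects are known to be declining, but the documents do not say so.

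**Chance imbalance is already in the standard error.** This is correct averaged over all trials, as step 6 shows. The distortion appears only in trials that happen to be imbalanced, and it is material only if the effect is large.

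**The precedent is thin.** On the sponsor's Phase 2b trial, Protocol 4.5 says: "Subjects were assigned to a study group based on their ESA status at screening". It does not say that the analysis adjusted for ESA status, and Protocol 6.3 models this trial on a different study.

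What remains is that a recorded, plausibly prognostic baseline variable goes unused when using it costs almost nothing.

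**Conclusion.** The point holds as a precision improvement of low severity. Prior ESA exposure is absent from the randomisation, the ANCOVA, the regression and the named baseline tables, although the trial records it and builds screening around it.

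The benefit depends on two assumed quantities, the share of recent ESA users and their effect on Hb change. For effects of 0.5-1.0 g/dL and shares of 25-75%, adjustment adds about 1 to 6 points of power for 600 mg v placebo. It also keeps type I error near 0.05 in trials that turn out imbalanced. If the share is 90% or more, or the effect is close to zero, little is gained.

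A reader might infer that the planned analysis is biased, that its type I error is inflated, or that the trial is underpowered. None of these follows: overall type I error stays at about 0.05, and the claim of more than 85% power is reproduced. A one-covariate ANCOVA is a defensible choice. The effect on the 150 and 300 mg contrasts cannot be sized, because the current text assumes no effects for those doses.

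**What to change.** Before unblinding for the Week 6 preliminary analysis:

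1. Define one binary baseline factor from the recorded last ESA dose date: ESA use within a fixed, pre-stated window before Day 1. The window should also catch former users enrolled under criterion 3a. A window shorter than 64 days would class every epoetin beta pegol subject washed out in screening as not recent. A simpler alternative is ESA washed out during screening, yes or no, accepting some misclassification. With 48 subjects, do not split by ESA class.
2. Add the factor to the Week 6 ANCOVA and the dose-response regression in SAP 4.7.1 and 4.7.2.1, and amend SAP 4.7.1.2 and Protocol 11.2 to match.
3. Keep the current models as sensitivity analyses.
4. Tabulate the factor by arm in SAP 4.5.

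**Cost.** No new data are needed. With all 48 subjects analysed, residual degrees of freedom fall from 43 (48 − 5) to 42. If the factor is unrelated to Hb change, power falls by about 0.03 percentage points by formula, or about 0.7 in simulation. Specified after unblinding, the term would look data-driven.
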